1. INTRODUCTION

1.1 Phase:

This is a pilot study to determine whether the addition of inspiratory hold (breath holding) can decrease the radiation dose that the heart receives for patients being treated for left sided breast cancer.

1.2 Indication:

Utilizing prone radiation therapy along with inspiratory hold to reduce the radiation dose to the heart and lungs.

1.3 Endpoints:

Primary

The primary endpoint is the feasibility of the breath-hold technique for women treated with radiation for left-sided breast cancer in the prone position.

Secondary

The secondary endpoint is to evaluate the changes in mean dose to the heart and lungs with prone breath hold. Other secondary endpoints include heart volume receiving 20 Gy, maximum dose to left ventricle/LAD artery and relative volumes of lung receiving 20 Gy.

1.4 Patient population:

Eligible subjects must be able to understand and sign the study specific subject consent form. They must be patients of [name] and ≥ 18 years of age. Eligible subjects must also have node-negative left breast cancer, invasive or DCIS breast cancer and have had a prior lumpectomy and deemed appropriate for treatment in the prone position by the treating physician. They must be able to tolerate breath-hold in the prone position.

2. STUDY DESIGN

2.1 Phase: This is a Pilot Study

2.2 Number of centers: One

This study will be performed by The University of Arizona Medical Center (UAMC) Radiation Oncology Department at both the University Campus Hospital and Orange Grove Clinic.

2.3 Number of subjects: Approximately 15

2.4 Subject participation time period:

Subjects will be enrolled in the study for 15 months, including screening time, treatment time, and follow-up at one year post radiation therapy.

Subjects enrolled in this study are undergoing treatment at UAMC Main Campus or Orange Grove Clinic as part of standard of care for the treatment of breast

cancer. Typical Radiation treatment schedule is between four and six weeks in length with treatments administered Monday through Friday.

SCHEMA

See Section 9.3

3. OBJECTIVES

3.1 Primary:

The primary endpoint is the feasibility of the breath-hold technique for women treated with radiation for left-sided breast cancer in the prone position.

3.2 Secondary:

To determine whether cardiac dose and lung dose can be reduced in women receiving prone breast radiotherapy when inspiratory gating is added. To evaluate the changes in mean dose to the heart and lungs with prone breath hold. Other secondary endpoints include heart volume receiving 20 Gy, maximum dose to left ventricle/LAD artery and relative volumes of lung receiving 20 Gy.

4. BACKGROUND and RATIONALE

4.1 Disease

4.2 There are currently estimated to be more than 2.8 million breast cancer survivors alive in the United States. Among these women, approximately 50% have received radiotherapy as part of their primary treatment. Adjuvant radiotherapy following lumpectomy improves both local control as well as overall survival. As such, whole breast radiotherapy following lumpectomy is the standard of care for women under 70. With advances in treatment, cure rates for early stage breast cancer now frequently exceed 95%. For these reasons, interventions aimed at reducing the long-term risks of radiotherapy are critical in this population as more survivors are living longer.

Late cardiac toxicity from breast radiotherapy is well documented. Early randomized studies from the 1970s and 80s comparing lumpectomy alone to lumpectomy plus radiotherapy demonstrated improved cause specific survival with the addition of radiotherapy. However, this cancer-specific survival benefit was negated by an increased risk of cardiac mortality 10-20 years following radiotherapy (Clarke et al 2005). While technical improvements in radiotherapy have dramatically reduced the risk of cardiac injury, recent studies have continued to demonstrate a small but significant increased risk of cardiovascular events following breast radiotherapy. Darby et al recently demonstrated that the risk of cardiac events following radiotherapy is directly proportional to the mean heart dose (Darby et al 2013). Thus, methods for reducing cardiac dose will be anticipated to reduce the long term risk of cardiac disease.

The two methods most frequently used to reduce cardiac dose during breast radiotherapy are prone positioning on a breast-board and inspiratory gated breath-

hold treatment. Lymberis et al prospectively studied 100 patients with CT simulation scans for RT planning in the prone and supine setups. It was found that prone position decreased the volume of lung within the radiation field in all patients and for left sided breast cancers 87% of patients had a decrease in irradiated volume of the heart. Formenti et al published their abstract of 200 patients with left-sided breast cancer who underwent radiotherapy treatment planning in both the prone and supine position. Radiation treatment plans for each position were compared specifically looking at doses to heart and lung volumes. Their results showed that prone positioning was associated with a 91.1% reduction in lung radiation dose and 85.7% reduction of in-field heart volume. A critique of the prone position is that due to gravity not only does the breast tissue fall away from the chest wall but the heart falls anteriorly towards the chest wall.

Remouchamp et al evaluated moderate deep-inspiration breath hold (DIBH) in external beam radiation treatment of left sided breast cancer. The treatment plans from the breath hold and free breathing CTs were compared showing a mean decrease of 3.6% of heart volume that received 30Gy. This would translate into a 1.5% decrease in the rate of heart normal tissue complication probability (NTCP). However, the absolute lung volume seeing higher doses of radiation is increased with DIBH but relative lung percentages receiving significant radiation doses may be improved. A retrospective study (Nissen et al 2013) reviewed 144 left-sided breast cancer patients treated with DIBH and 83 left-sided patients treated free breathing. The heart mean dose was decreased from 5.2 to 2.7Gy.

While both methods have independently been demonstrated to reduce cardiac dose and pulmonary dose, the combination of the two have not been reported. This study seeks to evaluate whether cardiac dose and pulmonary dose can further be reduced in women receiving prone breast radiotherapy with the addition of inspiratory gating. We anticipate that prone breath hold can further reduce radiation doses to these organs at risk, and potentially reduce the risk of late cardiovascular and pulmonary complications from breast radiotherapy.

If this study shows feasibility and potential for lowering cardiac and pulmonary dose for patients treated in the prone position with the addition of breath-hold then a larger randomized trial looking at optimal patient characteristics for this combined technique, further examining dose reductions using this experimental technique versus standard of care, and possible late toxicities, including cardiovascular and pulmonary, can be considered in the future.

4.2 Investigational Product:

Not applicable

4.3 Pre-clinical Experience

Not applicable

4.4 Clinical Experience

The two methods most frequently used to reduce cardiac dose during breast radiotherapy are prone positioning on a breast-board and inspiratory gated breath-hold treatment. Lymberis et al prospectively studied 100 patients with CT simulation scans for RT planning in the prone and supine setups. It was found that prone position decreased the volume of lung within the radiation field in all patients and for left sided breast cancers 87% of patients had a decrease in irradiated volume of the heart. Formenti et al published their abstract of 200 patients with left-sided breast cancer who underwent radiotherapy treatment planning in both the prone and supine position. Radiation treatment plans for each position were compared specifically looking at doses to heart and lung volumes. Their results showed that prone positioning was associated with a 91.1% reduction in lung radiation dose and 85.7% reduction of in-field heart volume. A critique of the prone position is that due to gravity not only does the breast tissue fall away from the chest wall but the heart falls anteriorly towards the chest wall.

Remouchamp et al evaluated moderate deep-inspiration breath hold (DIBH) in external beam radiation treatment of left sided breast cancer. The treatment plans from the breath hold and free breathing CTs were compared showing a mean decrease of 3.6% of heart volume that received 30Gy. This would translate into a 1.5% decrease in the rate of heart normal tissue complication probability (NTCP). However, the absolute lung volume seeing higher doses of radiation is increased with DIBH but relative lung percentages receiving significant radiation doses may be improved. A retrospective study (Nissen et al 2013) reviewed 144 left-sided breast cancer patients treated with DIBH and 83 left-sided patients treated free breathing. The heart mean dose was decreased from 5.2 to 2.7Gy.

While both methods have independently been demonstrated to reduce cardiac and lung dose, the combination of the two has not been reported. This study seeks to evaluate whether cardiac and lung dose can further be reduced in women receiving prone breast radiotherapy with the addition of inspiratory gating. We anticipate that prone breath hold can further reduce radiation doses to these organs at risk, and potentially reduce the risk of late cardiovascular and pulmonary complications from breast radiotherapy.

5. INVESTIGATIONAL PRODUCT

- 5.1 Investigational Product (IP)
Not Applicable
- 5.2 Investigational Product Supply
Not Applicable
- 5.3 Investigational Product Accountability
Not Applicable
- 5.4 Storage
Not Applicable

5.5 Preparation
Not Applicable

5.6 Handling
Not Applicable

6. SUBJECT ELIGIBILITY

Investigators will maintain an electronic subject log in the UACC OnCore and RedCao system of all potential (i.e. consented) study subjects, which will include as applicable (demographics, informed consent, eligibility, treatment assignment, on treatment, off treatment, follow up and off study dates).

6.1 Inclusion Criteria

1. Patients of [name]
2. ≥ 18 years of age
3. Node-negative left breast cancer
4. Invasive or DCIS breast cancer
5. Prior lumpectomy
6. Deemed appropriate for treatment in the prone position by the treating physician
7. Able to tolerate prone position and breath hold during CT simulation
8. Patient must be English speaking.

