7. STUDY PLAN

7.1 Treatment Regimen

Subjects will be recruited by [name] and [name] (or covering physician) at their standard of care appointment prior to the radiation planning appointment. Patients will be asked by [name] and [name] (or covering physician) if they are interested in participating in the study. If they are, a member of the research staff will review the study with the patient and complete the consent process. Subjects will be enrolled prior to their radiation therapy panning simulation (CT simulation).

During the radiation planning appointment, patients undergo CT scans used to plan the radiation doses and delivery. The number of images taken during the CT simulation is the same as if they were not treated on this research study. A CT scan will be performed in the prone position using coached voluntary inspiratory breath-holding using the RPM visual feedback system. Prone breath hold will be conducted using a monitor in the headrest of the prone breastboard that the subject will watch. This monitor allows the subjects to see their respiratory cycle which is a sinusoidal curve. Therapists coach the patient to hold their breath for approximately 15 seconds in order to maintain inspiration within a threshold bar set by the simulation therapists that is seen via the patient monitor. The purpose of the breath hold technique is to allow for optimal heart positioning for this study. This is the same method used for breath hold in the supine position which is considered standard of care. The reason this study is unique is because it is using the combination of prone positioning and inspiratory gated breath hold versus individually.

After the subject completes the radiation planning simulation, the physician will generate two radiation treatment plans: one for the free-breathing scan (standard of care) and one for the breath-hold scan (using inspiratory gating). For each plan, the heart, left ventricle/LAD artery and lungs will be contoured on each CT scan with radiation fields placed on both CT scans to dosimetrically determine heart, left ventricle/LAD artery and lung radiation doses and coverage of the affected breast. The doses to the heart, left ventricle/LAD artery and lungs will be compared to determine the plan with the lower cardiac and lung doses.

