At the discretion of the treating physician, the plan with the lower cardiac and lung doses will be used to treat the subject. Inspiratory breath hold will only be used if it results in lower cardiac and lung doses. If the free breathing plan shows

lower cardiac and lung doses, the patient will be treated per standard of care (prone without inspiratory breath hold). If the plan involves inspiratory breath hold, the subject will be notified by the research staff prior to the first day of treatment. Reasoning for treating a patient prone only versus prone and breath-hold will be documented by the treating physician. If the plan with inspiratory breath hold resulted in the lower cardiac and lung dose, inspiratory gating will be performed during each daily treatment. Treatment with breath hold adds approximately 5 minutes to the overall setup and treatment time of each daily treatment. During daily radiation, prone breath hold will be conducted using a monitor below the prone headrest that the patient will watch. This monitor allows the patient to see their respiratory cycle and indicates the amount of inhalation that would be required (threshold bar represented as a blue box) in order to allow for treatment that is representative each day of their initial simulation CT scan. This monitor allows the subjects to see their respiratory cycle which is somewhat of a sinusoidal curve. Therapists coach the patient to hold their breath for approximately 15 seconds in order to maintain inspiration within a threshold bar (blue box) set by the simulation therapists that is seen via the patient monitor. During treatment, the radiation beam is only active when the patient breath hold is within the threshold bar on the monitor. The radiation treatment machine is set to turn off when the breath hold is outside of this threshold bar (blue box).

The physician will complete an evaluation form (RTOG CF form attached) regarding cardiac co-morbidities. The form will be completed at baseline (radiation planning session) and at 6 months post RT, and then at 1 year. This will not require any additional time for the subject and will be based on the information gathered by the physician at the standard of care appointment.

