8.2 Dose/treatment modification
Not applicable

- 8.3 Investigational Product Dose Delay
Not Applicable
- 8.4 Definition of a Dose Limiting Toxicity (DLT)
Not Applicable

9. STUDY PROCEDURES (the actual procedures need to be entered below and/or in a study schema/calendar – see my note in section # 26)

- 9.1 Screening
Potential subjects will enter the screening period of the study after completely executing a study specific informed consent form.
- 9.2 Registration/Randomization
Once this study is approved by all internal regulatory agencies to enroll subjects, study enrollment will begin. Subjects will be entered into the study. Subjects will be identified by their initials (First, Middle if available, Last) and a study number. Study numbers will begin with GO-B-001 and continue sequentially.
The subject CT Simulation will be scheduled.
- 9.3 On Intervention: Subjects will undergo the standard of care CT simulation, which includes an additional breath hold CT. Inspiratory gated breath-hold will be used. Two radiation plans will be generated: one for the CT scan performed free breathing, and one for the scan performed with inspiratory gated breath hold. The cardiac and lung doses will be determined. At the discretion of the treating physician, the plan with the lower cardiac and lung dose may be used to treat the patient.
- 9.4 End of Intervention: The intervention will be considered complete at the time the patient's treatment plan has been generated.
- 9.5 Follow up
Subjects will be seen for one 30 day [± 10 days] follow-up visit after the end of RT then at 6 months (± 30 days) and then at one year (± 30 days) from the end of radiation therapy. These visits are part of RT standard of care. During each of these visits, patients will be asked about any cardiac or pulmonary changes, including any cardiac or pulmonary symptoms [i.e. shortness of breath, rapid heart beat, chest pain, and whether or not they have had any cardiac or pulmonary testing (i.e. ECG, echo, muga or PFTs)].
- 9.6 Early intervention termination
Not Applicable
- 9.7 Off study

Subjects will be considered off study after completing their one year (+/- 30 days) post RT follow-up visit. Subjects will also be considered off study if they chose to voluntarily withdraw from the study. They will be asked to be seen for a final end

of study follow-up that would include the same procedures as the follow-up appt. described in Section 9.5.

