16. STASTISITICAL CONSIDERATIONS

Statistical analysis will be performed in collaboration with [name], the Director of the University of Arizona Cancer Center Biometry Shared Service.

The primary endpoint of the study is the feasibility of the breath-hold technique for women treated with radiation for left-sided breast cancer in the prone position. Although it is expected that the number of women who are unable to master the breath-hold technique will be small, the proportion of women who cannot master the technique will be estimated with the appropriate exact 95% confidence interval.

The secondary endpoint is to evaluate the changes in the mean dose to the heart and lungs with prone breath hold. Each woman enrolled in the study will have two radiation plans generated in the prone position: one for the free-breathing scan and one for the breath-hold scan. The mean difference between the dosimetrically determined heart and lung radiation doses will be computed with the associated 95% confidence interval. A paired t test will be used to assess

whether the mean difference is statistically significant. The other secondary endpoints will be analyzed in a similar fashion.

Ten women will give 80% statistical power to detect a difference of 1 standard deviation unit in the mean dose between the two conditions. Note that since paired data will be generated, the number of women required is less than if two independent samples of women were to be used. Additionally, the percentage of women in which adding the breath-hold results in a lower cardiac and lung dose will be estimated with standard error of 16% or less. The estimated mean difference (and its standard error) will be used to generate the sample size required for a larger study to statically assess the benefit of adding the breath-hold in reducing the cardiac and lung radiation dose.

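### Tolerating breath hold at simulation is an eligibility criterion, yet failing breath hold is the primary outcome, so failures can drop out of the primary estimate

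*Combined protocol and SAP*

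**What the plan says.** **Eligibility.** Criterion 7 in section 6.1 reads "Able to tolerate prone position and breath hold during CT simulation". Section 1.4 repeats it without naming the simulation: "They must be able to tolerate breath-hold in the prone position".

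**Primary estimate.** Section 16 states that "the proportion of women who cannot master the technique will be estimated with the appropriate exact 95% confidence interval". It expects the number of such women to be small but gives no figure, no denominator and no definition of mastering the technique.

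**Order of events.** Section 7.1 enrols women before the planning CT. Section 9.2 registers and numbers them, and only then says "The subject CT Simulation will be scheduled". The log in section 6 is kept "of all potential (i.e. consented) study subjects" and records eligibility among its items.

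**Two radiation plans.** Section 16 also says that every enrolled woman will have two radiation plans, one from the free-breathing scan and one from the breath-hold scan.

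**When breath hold stops counting.** Section 9.4 says "The intervention will be considered complete at the time" the treatment plan has been generated. Under section 7.1, if the breath-hold plan gave the lower doses, "inspiratory gating will be performed during each daily treatment".

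**The concern.** The event that the primary endpoint counts is largely the event that makes a woman ineligible. If women who fail at simulation are treated as ineligible, the reported proportion describes a group already selected for being able to do the manoeuvre, and its confidence interval carries the same selection. If they are kept, the same trial yields a higher failure proportion. The protocol does not say which applies, so the choice could be made after the results are known.

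This matters beyond the pilot. The background in section 4 makes a larger randomized trial depend on this study showing feasibility. The denominator question also affects a second figure in section 16, the percentage of women in whom breath hold lowers the heart and lung dose.

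**Working it through.** **1. Which reading does the text support?**

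| Points toward counting simulation failures | Points toward leaving them out |
|---|---|
| Enrolment precedes simulation (7.1, 9.2) | Criterion 7 (6.1) and section 1.4 |
| All consented women are logged (6) | Consent opens a screening period (9.1) and the log records eligibility (6), so a failure can be handled as a screen failure |
| Section 16 expects a few women who cannot master the technique | Section 16 gives every enrolled woman a breath-hold plan, which is impossible without a breath-hold scan |

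Neither column settles the matter. Section 16 supports both.

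**2. Direction of the bias.** Let *s* be the failure rate at simulation and *d* the later failure rate among women who passed simulation. The failure rate among all who attempt is *s* + (1 − *s*)*d*. Strict use of criterion 7 estimates *d* alone. The difference, *s*(1 − *d*), is positive whenever *s* > 0 and *d* < 1, so the shift can only be downward. With assumed values:
- *s* = 10%, *d* = 10%: 10% is estimated instead of 10% + 0.9 × 10% = 19%.
- *s* = 20%, *d* = 5%: 5% is estimated instead of 20% + 0.8 × 5% = 24%.

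If section 9.4 also closes the observation period at plan generation, later failures are not counted either, and the estimate is close to zero by construction.

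**3. Size with 15 women.** Section 2.3 plans about 15 subjects. The failure counts are assumptions. Intervals are exact (Clopper-Pearson) 95%. For zero events the upper limit is 1 − 0.025^(1/*n*).

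| Failures at simulation | Counted | Excluded, no later failures |
|---|---|---|
| 1 | 1/15 = 6.7% (0.2–31.9) | 0/14 = 0% (0–23.2) |
| 2 | 2/15 = 13.3% (1.7–40.5) | 0/13 = 0% (0–24.7) |
| 3 | 3/15 = 20.0% (4.3–48.1) | 0/12 = 0% (0–26.5) |
| 4 | 4/15 = 26.7% (7.8–55.1) | 0/11 = 0% (0–28.5) |
| 5 | 5/15 = 33.3% (11.8–61.6) | 0/10 = 0% (0–30.8) |

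If failures were replaced until 15 women passed, which the protocol does not state, 3 failures would give 3/18 = 16.7% (3.6–41.4) counted, against 0/15 = 0% (0–21.8) excluded.

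**4. Sensitivity to when failures happen.** Take 3 failures in total among 15 women, where counting them all gives 20.0%:

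| At simulation | Later | Strict exclusion gives |
|---|---|---|
| 3 | 0 | 0/12 = 0% (0–26.5) |
| 2 | 1 | 1/13 = 7.7% (0.2–36.0) |
| 1 | 2 | 2/14 = 14.3% (1.8–42.8) |
| 0 | 3 | 3/15 = 20.0% (4.3–48.1), no bias |

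**5. How likely is at least one simulation failure?** This is 1 − (1 − *s*)^15. For assumed *s* of 5%, 10% and 20% it is 54%, 79% and 96%.

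**6. The percentage who benefit.** If 3 of 15 fail and 9 of the other 12 have a lower dose, the result is 9/12 = 75.0% (42.8–94.5) or 9/15 = 60.0% (32.3–83.7), depending on the denominator.

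**7. Does the paired comparison survive a change of denominator?** Section 16 claims 80% power with 10 women for a difference of 1 standard deviation. A paired *t* test with *n* = 10 and two-sided alpha 0.05 (assumed; the protocol does not state it) gives 80.3% from the noncentral *t* distribution, so the claim reproduces. With 15 women, up to 15 − 10 = 5 simulation failures still leave those 10 pairs.

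**The case against.** The strongest reply is that the protocol already leans toward counting these women. They are enrolled, numbered and logged before simulation. Section 9.7 gives only two routes off study, the one-year visit or voluntary withdrawal, and failing breath hold is neither. Section 15 keeps even a withdrawn woman's data up to withdrawal. No passage removes or replaces a woman who fails. This stands, and it is why the bias is a risk and not a certainty. It does not override an explicit inclusion criterion or the statement that every enrolled woman has a breath-hold plan.

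A second reply is that *tolerate* and *master* may differ: a woman might manage the position and the attempt without holding steadily within the threshold. On that reading some failures stay in the estimate. That reduces the bias but does not remove it, and the protocol defines neither word.

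Third, the failure counts are assumed, the larger ones fit poorly with an expectation of few failures, and at 1 failure the two intervals overlap heavily. No numerical feasibility threshold is set, so no stated decision rule changes. All of this is correct and limits what can be said about size. It does not affect the direction.

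Finally, the data collection form is not reproduced, so what is recorded about breath-hold performance cannot be judged. A form would not in any case settle the denominator.

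**Conclusion.** The concern holds and should be fixed before analysis. One stated rule, applied as written, removes from the primary estimate the event that it is meant to count, and the resulting shift can only be toward zero. The size cannot be derived from the protocol. With 15 women attempting, all failures at simulation and none later, 1 to 5 failures would be reported as 0% instead of 6.7% to 33.3%. The gap narrows as more failures fall after simulation and disappears if none occur there. The conclusion rests on criterion 7 being enforced and on *tolerate* and *master* overlapping substantially. The protocol leaves both open.

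**What to change.** Reconcile sections 1.4, 6.1, 7.1, 9.2, 9.4 and 16 so that breath-hold tolerance does not decide who enters the primary analysis. Either remove it from eligibility or keep it only as the condition for the paired dose comparison. Then state in section 16:

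1. The primary denominator is all consented women who attempt prone breath hold at simulation.
2. Failure to master means not completing the breath-hold scan with the coached hold that section 7.1 already describes. Each such woman counts as a failure and is not replaced in this analysis.
3. Whether failures during daily treatment also count. If they do, report them separately over the women who start breath-hold treatment.
4. Paired dose analyses use women with both scans, in place of the statement that every enrolled woman has two radiation plans.
5. The percentage who benefit is reported over all women who attempted, with failures counted as no benefit, alongside the percentage among women with both scans.

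The cost is a short amendment. It adds no procedures or patients and, with up to 5 simulation failures among 15 women, leaves the power statement for the paired comparison intact. The reported feasibility may look less favourable.
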